## 1. Summary/Hypothesis

Children with high grade gliomas (HGG) including glioblastoma multiforme and anaplastic astrocytoma have expected overall survival rates of less than 35% at 3 years despite best available therapies. Unfortunately, most patients succumb to their disease. Additionally, most recurrent pediatric central nervous system tumors (CNS) are characterized by aggressive clinical behavior. Children with refractory or recurrent CNS tumors are generally considered to have lower overall survival. There is an urgent need for newer and innovative therapeutic options.

These include novel biologically driven treatments that have potential to extend and improve the survival of these patients. Cabozantinib is a novel tyrosine kinase inhibitor of VEGFR2, RET, and MET which shows promising response rates in adults with high grade gliomas. It is FDA approved for medullary thyroid cancer and has safety and toxicity data with recommended dosing for children. There is strong biological and clinical evidence that this treatment may improve outcomes. This pilot will study the feasibility and exploratory efficacy of using this agent for recurrent or refractory central nervous system tumors. Patients will also be followed for safety, time to progression, event free survival and overall survival. If successful, this study will support the development of an expanded multi-institutional efficacy trial in children with high grade glial tumors and other aggressive brain tumors.

## 2. Background and Rationale

[figure not shown]
Children with high grade gliomas including glioblastoma multiforme (GBM) and anaplastic astrocytoma (AA), have expected overall survival rates less than 35% despite our best available therapies. Numerous other histologic subtypes of pediatric central nervous system tumors have worse overall survival at recurrent. Additionally, most recurrent pediatric CNS tumors are characterized by aggressive clinical behavior. High grade gliomas are classified by the World Health Organization (WHO) as either grade III or IV meaning that they are highly malignant tumors with characteristic findings such as hypercellularity, nuclear atypia, and high mitotic activity with or without microvascular proliferation and pseudopalisading necrosis. High-grade gliomas include a variety of heterogeneous tumors with differing histologies, but the most common histologies are anaplastic astrocytoma and glioblastoma multiforme. Although there truly is no one accepted standard of care and treatment algorithms can vary, most experts agree that a gross total resection (GTR) followed by focal irradiation to the tumor bed plus additional

V 5.0 March 5, 2021 IUSCC-0601

chemotherapy is an appropriate treatment approach. However, with such an approach, Progression Free Survival (PFS) in patients with GTR is 35% compared to 17% with subtotal resection of tumor. Patients with recurrent disease approach mortality rates of 100%. Therefore, much work remains to be done to improve survival in these patients.

Other histologic subtypes of aggressive childhood brain tumors follow a similar pattern to high grade gliomas. Children with medulloblastoma, ependymoma, atypical teratoid rhabdoid tumor and diffuse intrinsic pontine glioma often face challenges with overall survival both at diagnosis and at recurrence. Similar to high grade glioma, most of these tumors have no accepted standard of care at relapse/recurrence. Therefore, determining potential opportunities to improve outcomes for these children is pivotal.

Cabozantinib (also known as XL184 and Cometriq) is an ATP-competitive inhibitor of c-MET, VEGFR2, and RET and falls into the category of drugs called tyrosine kinase inhibitors. This drug also inhibits KIT, AXL, and FLT-3, all of which have been implicated in tumor pathogenesis. Amplification of the c-MET gene is seen in glioblastomas and both c-MET and HGF are frequently overexpressed in glioma specimens and cell lines. Treatment with cabozantinib-inhibited MET and VEGFR2 phosphorylation *in vitro* and in tumor models *in vivo* led to significant reduction in cell invasion. In mouse models, cabozantinib dramatically altered tumor pathology, resulting in decreased tumor and endothelial cell proliferation coupled with increased apoptosis and dose-dependent inhibition of tumor growth in breast, lung, and glioma tumor models. VEGF or vascular endothelial growth factor has been targeted as a potent inhibitor of angiogenesis. However, selective inhibition of this target has only yielded in modest short-lived response in high grade gliomas. MET which is postulated to a mechanism of resistance to VEGF inhibition, activates downstream tumorigenic pathways such as PI3K and ERK pathways. Therefore, therapies which target both VEGF and MET might be a promising approach against glioblastoma.

Evaluation of cabozantinib in pediatric brain tumor models has suggested potential clinical activity. In an *in vitro* cell line from a pediatric Diffuse Intrinsic Pontine Glioma patient there was both synergy in the antiproliferative effect when combined with dasatinib and the inhibition of cell invasion in an inherently dasatinib-resistant cell line. The rate of c-MET amplification in pediatric GBM ranges from 0% to 44% based on genome-wide copy number. Additionally, there is evidence that targeting MET and VEGFR2 simultaneously suppresses metastasis, angiogenesis, and tumor growth.

## 2.2 Clinical Summary

A promising Phase 2 study in adult patients with progressive glioblastoma in first or second relapse showed 38% radiologic response of >50% reduction in tumor size by imaging (ASCO abstract 2047 at ASCO 2009). There was also evidence of decreased corticosteroid use and consistent reduction in edema at Day 28. Dosage on that study was 175 mg daily by mouth and 125 mg daily dosing is currently under investigation to allow for better tolerability. This would translate to 140 mg and 100 mg Free base equivalent.

A Pediatric Phase I safety, dosing, and tolerability trial has been completed by the Children's Oncology Group (COG) in children with refractory solid tumors and presented at ASCO 2014. Based on this study, the investigators recommended a Phase 2 dosing of 40 mg/m^2 daily which is equivalent to 72 mg adult dose. Common toxicities noted with this drug included diarrhea, stomatitis, weight loss, anorexia, nausea, fatigue, oral pain, hair color changes, dysgeusia, hypertension, abdominal pain, and constipation. Dose limiting toxicities (DLT) included lipase elevation, palmar-plantar erythrodysesthesia

syndrome (PPE), and mucositis. Rare serious Adverse Events (AE) may include venous thromboembolism. Response data from this trial has not been made available.

Cabozantinib is currently FDA approved and commercially available for the treatment of medullary thyroid cancer and advanced renal cell carcinoma. Cabozantinib is a good candidate for central nervous system (CNS) malignancies because there is evidence that it crosses the blood brain barrier. Analysis of whole-brain lysates of non-tumor-bearing mice indicated that cabozantinib attained 20% of peak plasma levels, demonstrating the ability of the drug to penetrate the blood-brain barrier (Investigational Brochure version 12).

To date, there have been 17 clinical studies of cabozantinib for oncology indications including four Phase 1 studies, one Phase 1b/2 study, four Phase 2 studies, five Phase 3 studies (a placebo-controlled study in subjects with MTC, two active-controlled studies in subjects with castration-resistant prostate cancer [CRPC], one ongoing open-label, active-controlled study in subjects with RCC, and one ongoing and enrolling double-blinded placebo-controlled study in subjects with hepatocellular carcinoma [HCC]), one ongoing and enrolling Phase 4 study in MTC, one ongoing maintenance “roll-over” study, and one expanded access study. In addition, there are eleven clinical pharmacology studies; nine were conducted in healthy subjects alone, one study was conducted that included healthy subjects and subjects with renal impairment, and one study was conducted that included healthy subjects and subjects with hepatic impairment. In addition to these company-sponsored clinical studies, twenty-six investigator-sponsored trials (ISTs) and sixteen National Cancer Institute (NCI)-Cancer Therapy Evaluation Program (CTEP) trials have enrolled subjects in oncology indications. (Investigator Brochure version 12).

A tablet dose of 60 mg once daily (qd) was evaluated in two Phase 3 studies in prostate cancer, and two ongoing Phase 3 studies, one in RCC and one in HCC, are also evaluating this dose. Ongoing double-blind Study XL184-401 compares the efficacy and safety of cabozantinib 140 mg qd (capsule formulation) with cabozantinib 60 mg qd (tablet formulation). Common to all studies is the titration of the dose to individual patient tolerability.

### 2.2.3 Clinical Safety Profile

Across company-sponsored studies with single-agent cabozantinib, the most frequently observed AEs ( $\geq 20\%$  of subjects), regardless of causality, are shown in Table 2-1.

**Table 2-1: Summary of Adverse Events Experienced by  $\geq 20\%$  of Subjects Treated with Single-Agent Cabozantinib, N = 2410**

MedDRA Preferred Term	All AEs		Related AEs	
	Subjects with AE n (%)	Subjects with $\geq$ Grade 3 AE	Subjects with AE n (%)	Subjects with $\geq$ Grade 3 AE
Number of subjects with at least one	2404 (99.8)	1979 (82.1)	2324 (96.4)	1512 (62.7)
Diarrhoea	1471 (61.0)	251 (10.4)	1300 (53.9)	226 (9.4)
Fatigue	1458 (60.5)	369 (15.3)	1281 (53.2)	312 (12.9)
Nausea	1290 (53.5)	118 (4.9)	1062 (44.1)	89 (3.7)
Decreased appetite	1283 (53.2)	136 (5.6)	1080 (44.8)	104 (4.3)
Vomiting	861 (35.7)	95 (3.9)	612 (25.4)	59 (2.4)
Weight decreased	860 (35.7)	97 (4.0)	671 (27.8)	75 (3.1)
Palmar-plantar erythrodysesthesia	835 (34.6)	186 (7.7)	819 (34.0)	185 (7.7)
Constipation	779 (32.3)	31 (1.3)	345 (14.3)	11 (0.5)
Hypertension	708 (29.4)	330 (13.7)	603 (25.0)	284 (11.8)
Dysgeusia	637 (26.4)	2 (0.1)	605 (25.1)	2 (0.1)
Dysphonia	610 (25.3)	5 (0.2)	520 (21.6)	4 (0.2)
Asthenia	557 (23.1)	165 (6.8)	434 (18.0)	124 (5.1)
Dyspnoea	497 (20.6)	76 (3.2)	187 (7.8)	22 (0.9)

AE, adverse event; MedDRA, Medical Dictionary for Regulatory Activities.

Note: Reported AEs were coded using MedDRA version 17.0. At each level of summarization, a subject is counted only once if the subject reported one or more events.

Note: This table summarizes pooled data in the clinical database for single-agent cabozantinib studies (XL184-001, XL184-008, XL184-201, XL184-203, XL184-205, XL184-301 cabozantinib arm, XL184-306 cabozantinib arm, XL184-307 cabozantinib arm, XL184-308 cabozantinib arm, and XL184-401).

As of 29 February 2016, the incidence of Grade 5 AEs from pooled single-agent studies was 10.5% (254 subjects). The Grade 5 AEs that occurred at  $\geq 1\%$  frequency were prostate cancer (2.9%) and general physical health deterioration (1.0%). Only one of these events (an event of general physical health deterioration on Study XL184-307) was assessed as related to study treatment, and per convention prostate cancer was the preferred term (PT) for disease progression of the cancer under study. Thirty-three (33) subjects had Grade 5 AEs that were assessed as related to study treatment. The only related Grade 5 AEs that occurred more than once were pulmonary embolism (n=4), death (unspecified; n=3), hemorrhage (n=2), respiratory failure (n=2), and sudden death (n=2). In the ongoing company-sponsored double-blind Study XL184-309 (N = 450) in subjects with advanced HCC, 58 Grade 5 AEs (regardless of causality) were reported as of 29 February 2016.

The most commonly reported SAEs (experienced by  $\geq 1\%$  of subjects), regardless of causality, are shown in Table 2-2.

**Table 2-2: Summary of Serious Adverse Events Experienced by  $\geq 1\%$  of Subjects Treated with Single-Agent Cabozantinib Excluding Events of Disease Progression, N = 2410**

MedDRA Preferred Term	All SAEs		Related SAEs	
	Subjects with SAE	Subjects with $\geq$ Grade 3 SAE	Subjects with SAE	Subjects with $\geq$ Grade 3 SAE
	n (%)	n (%)	n (%)	n (%)
Subjects reporting at least one SAE	1332 (55.3)	1221 (50.7)	602 (25.0)	516 (21.4)
Pulmonary embolism	120 (5.0)	119 (4.9)	85 (3.5)	84 (3.5)
Vomiting	81 (3.4)	48 (2.0)	40 (1.7)	27 (1.1)
Nausea	72 (3.0)	44 (1.8)	47 (2.0)	31 (1.3)
General physical health deterioration	71 (2.9)	65 (2.7)	13 (0.5)	9 (0.4)
Dehydration	69 (2.9)	54 (2.2)	41 (1.7)	32 (1.3)
Pneumonia	69 (2.9)	58 (2.4)	5 (0.2)	4 (0.2)
Anaemia	59 (2.4)	49 (2.0)	17 (0.7)	13 (0.5)
Abdominal pain	53 (2.2)	43 (1.8)	13 (0.5)	9 (0.4)
Diarrhoea	52 (2.2)	36 (1.5)	42 (1.7)	31 (1.3)
Deep vein thrombosis	46 (1.9)	36 (1.5)	21 (0.9)	16 (0.7)
Fatigue	43 (1.8)	36 (1.5)	27 (1.1)	25 (1.0)
Asthenia	41 (1.7)	30 (1.2)	20 (0.8)	13 (0.5)
Back pain	41 (1.7)	36 (1.5)	1 (0.0)	1 (0.0)
Dyspnoea	39 (1.6)	26 (1.1)	7 (0.3)	5 (0.2)
Pyrexia	36 (1.5)	9 (0.4)	5 (0.2)	2 (0.1)
Urinary tract infection	35 (1.5)	25 (1.0)	4 (0.2)	3 (0.1)
Hyponatraemia	31 (1.3)	29 (1.2)	15 (0.6)	14 (0.6)
Pleural effusion	30 (1.2)	22 (0.9)	6 (0.2)	5 (0.2)
Renal failure acute	30 (1.2)	24 (1.0)	7 (0.3)	5 (0.2)
Convulsion a	29 (1.2)	18 (0.7)	5 (0.2)	2 (0.1)
Decreased appetite	28 (1.2)	20 (0.8)	19 (0.8)	14 (0.6)
Bone pain	27 (1.1)	23 (1.0)	0	0
Sepsis	27 (1.1)	27 (1.1)	5 (0.2)	5 (0.2)
Metastatic pain	26 (1.1)	20 (0.8)	1 (0.0)	0
Confusional state	25 (1.0)	17 (0.7)	7 (0.3)	5 (0.2)
Constipation	25 (1.0)	9 (0.4)	9 (0.4)	4 (0.2)
Spinal cord compression	23 (1.0)	22 (0.9)	1 (0.0)	1 (0.0)

---

MedDRA, Medical Dictionary for Regulatory Activities; SAE, serious adverse event.

Note: Reported SAEs were coded using MedDRA version 17.0. At each level of summarization, a subject is counted only once if the subject reported one or more events.

Note: This table summarizes pooled data from the safety database for single-agent cabozantinib studies (XL184-001, XL184-008, XL184-201, XL184-203, XL184-205, XL184-301 cabozantinib arm, XL184-306 cabozantinib arm XL184-307 cabozantinib arm, XL184 308 cabozantinib arm, and XL184-401).

Note: Disease progression is expected for subjects with advanced cancer on cabozantinib clinical trials, and as such, events of progression of underlying cancer are not included.

a Twenty out of 29 of the observed convulsion events were reported in subjects with glioblastoma (GB) enrolled in Studies XL184-201 or XL184-205. For more information on safety observed in subjects with GB, see Section 4.3.1.

The primary aim of this proposed trial is to evaluate the safety and exploratory efficacy signal of this agent as a therapy in recurrent central nervous system tumors. There is biological evidence that the targets of this drug are present and relevant in glioblastoma multiforme, anaplastic astrocytoma, and diffuse intrinsic pontine glioma, all of which are conditions with a dismal prognosis. Subjects on study will have routine safety evaluations of complete blood counts, complete metabolic panel, and 12 lead ECGs. All subjects will be followed closely for safety and tolerability. Therapy will be discontinued if there is evidence of tumor progression.

### 3. Specific Aims

**Primary Safety Aim:** Assess the safety and tolerability of cabozantinib in refractory and/or recurrent central nervous system tumors who have previously received prior treatment, including radiation therapy.

**Primary Efficacy Aim:** Assess the disease control rate (CR, PR, or SD for at least 6 months of cabozantinib in refractory and/or recurrent pediatric central nervous system tumors who have previously received prior treatment, including radiation therapy.

#### **Secondary Aims:**

1. Assess the 6 month progression free survival (PFS) in subjects with refractory or recurrent central nervous system tumors who have previously received prior treatment, including radiation therapy treated with cabozantinib
2. Assess the utilization of corticosteroid use in subjects with recurrent or refractory central nervous system tumors treated with cabozantinib

3. Assess the objective response rate of target lesion in subjects with recurrent or refractory central nervous system tumors treated with cabozantinib
4. Assess the overall survival (OS) rate at 6 months and 12 months in subjects with refractory or recurrent central nervous system tumors treated with cabozantinib
5. Assess the 12 month PFS in subjects with refractory or recurrent central nervous system tumors treated with cabozantinib.

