#### 4.2 Dose, Schedule and Route

Study medication will be taken daily at a dose of 40 mg/m^2. Drug cycles will last 28 days and be continuous for up to 12 months of therapy on study.

Cabozantinib will be held for subjects who experience toxicity until the toxicity has decreased to grade 1. Cabozantinib will then be reduced by one dose level and not re-escalated in subsequent cycles. Subjects who experience toxicity at dose level -1 will be off study (See Section 7.0 for Dose Modification guidelines).

Dose Level	Dose (mg/m  /dose with max dose 60 mg/day)
-1	30 mg/m 
1	40 mg/m 

Actual dosing will be based on dosing nomogram in Appendix VI

Cabozantinib must be taken on an empty stomach. Subjects must be instructed not to eat for at least 2 hours before and at least 1 hour after taking cabozantinib. Subjects should be instructed to take their cabozantinib dose at approximately the same time every day. If a subject misses a dose, the dose may be taken later only if it is within 12 hours of when the missed dose should have been taken. The missed dose should not be made up if it is within 12 hours of the next scheduled dose.

Cabozantinib tablets should be swallowed whole with at least 8 ounces of water. The tablets should not be crushed. Grapefruit, grapefruit juice, Seville oranges and their products should be avoided by subjects taking cabozantinib.

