## 7. Study Procedures

**Pre-study evaluations:** The investigational nature and objectives of the trial, the procedures and treatments involved and their attendant risks and discomforts and potential alternative therapies will be carefully explained to the patient and or the patient's parent(s) or guardian if the patient is a child, and a signed informed consent and assent will be obtained according to institutional and federal guidelines.

Diagnostic or laboratory studies performed exclusively to determine eligibility for this trial must only be done after obtaining written informed consent. Documentation of the informed consent for screening will be maintained in the subject's research chart. Studies or procedures that were performed for clinical indications (not exclusively to determine eligibility) may be used for baseline values even if the studies were done before informed consent was obtained.

Within 14 days of starting study drug, pre-study evaluations include: History and physical exam, laboratory studies, performance status, pregnancy test (for females of child bearing age), 12-lead ECG and MRI of brain +/- spinal cord.

**Criteria for Starting Subsequent cycles:** A cycle may be repeated every 28 days(+/- 3 days) if the subject does not have evidence of progressive disease and has again met laboratory parameters as defined in the eligibility criteria, with the exception of ANC, which must be  $\geq 1000/\text{mm}^3$  to start each cycle.

History and physical exam, laboratory studies, performance status, study drug and corticosteroid drug diaries will be collected every 15 days (+/- 72 hours) after initiation of drug for cycles 1-3.

History and physical exam, laboratory studies, performance status, study drug and corticosteroid drug diaries will be collected every 28 days (+/- 72 hours) for cycles 4-12.

MRI's will be performed every 3 months (+/- 1 week).

12-lead ECG will be performed at pre-study, End of Cycle 1, End of Cycle 3 and End of Cycle 6, unless additional ECGs are required per protocol guidance (dose modification or concomitant medication usage)

Study Schedule: STUDIES TO BE OBTAINED	Pre-Study 	Cycle 1 ^	Cycle 2, 3 ^	Cycle 4-12 ^	Completion of Study
Informed Consent obtained	X				
History (including Con Meds)	X	Day 28	Days 15, 28	Day 28	X
Physical exam with vital signs and pulse ox	X	Days 15 and 28	Days 15, 28	Day 28	X
Height, weight, BSA	X	Day 28	Days 15, 28	Day 28	X

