Blood pressure 	X	Days 15 and 28	Days 15, 28	Day 28	X
Performance Status	X	Day 28	Days 15, 28	Day 28	X
Subject Diaries (Study drug and steroid use)	X	Day 15 & 28	Day 15 & 28)	Day 28	X
CBC, differential, platelets	X	Days 15 and 28	Days 15, 28	Day 28	X
CMP  with Ca, Mg, Phos, lipase, amylase	X	Days 15 and 28	Days 15, 28	Day 28	X
PT, PTT, INR	X	Day 28	Day 28	Day 28	X
Urinalysis	X	Day 28	Day 28	Day 28	X
Urine protein/creatinine	X	Day 28	Day 28	Day 28	X
Pregnancy test 	X 		Day 28 Cycle 2	Day 28 Cycles 4, 6, 8, 10, 12	X
Thyroid stimulating hormone	X	Day 28	Day 28 Cycle 3	Day 28 Cycles 6, 9, 12	X
12- lead ECG 	X	Day 28	Day 28 Cycle 3	Day 28 Cycles 6	
MRI of brain +/- spinal cord if clinically indicated 	X		Day 28 Cycle 3	Day 28 Cycles 6 and 9	X
Assess for adverse events		x	x	x	x

^ Studies may be obtained within +/- 72 hours unless otherwise specified within the table

1. All studies to determine eligibility must be performed within 2 weeks prior to enrollment. Consent must be obtained prior to enrollment but does not expire at 2 weeks.

2. Baseline BP should be obtained by collecting 3 serial BP measurements at least 5 minutes apart and then averaging the second and third BP measurements.

3. CMP should include: sodium, potassium, chloride, bicarbonate, blood urea nitrogen, creatinine, glucose, albumin, total protein, SGOT (AST), SGPT (ALT), total bilirubin, alkaline phosphatase

4. For females of childbearing age

5. If the subject starts a medication with substantial evidence that the drug prolongs the QT interval, then ECG monitoring must be performed at the end of each cycle while on the medication

6. For subjects with Complete or Partial response confirmatory MRI per RANO criteria will be performed within 6 weeks. For scheduling purpose, obtain within +/- 1 week of required observation

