#### 14.6 Efficacy Analysis

The efficacy set will be used for all the efficacy analysis. For the primary efficacy aim of the disease control rate (CR, PR, or SD for at least 6 months), an estimate will be determined along with the corresponding exact 95% binomial confidence interval. A similar analysis will be done for the secondary objective of objective response rate (CR, PR).

For PFS and OS, the median and their corresponding two-sided 95% confidence intervals will be calculated using the Kaplan-Meier method. Estimates and 95% confidence intervals will also be provided for 6 and 12 months.

A listing of the patients who used corticosteroid will be provided.

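### MRI timing is set both by 28-day cycle and by calendar month, and the final scan has no date, so assessment at 6 and 12 months is not secured

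*Combined protocol and SAP*

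**What the plan says.** **Endpoints.** Section 3 lists as its last secondary aim: "Assess the 12 month PFS in subjects with refractory or recurrent central nervous system tumors treated with cabozantinib". The primary efficacy aim counts complete response, partial response, or stable disease lasting at least 6 months, and another secondary aim is 6-month PFS. Section 14.6 uses Kaplan-Meier for PFS and adds: "Estimates and 95% confidence intervals will also be provided for 6 and 12 months".

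**Treatment calendar.** Section 4.2: "Drug cycles will last 28 days and be continuous for up to 12 months of therapy on study". Section 7 gives a start window for each cycle ("A cycle may be repeated every 28 days(+/- 3 days"), and its per-cycle visits stop at Cycle 12 ("study drug and corticosteroid drug diaries will be collected every 28 days (+/- 72 hours) for cycles 4-12").

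**Imaging, in the text of Section 7.** "MRI's will be performed every 3 months (+/- 1 week".

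**Imaging, in the table of Section 7.** The row "MRI of brain +/- spinal cord if clinically indicated" is marked at pre-study, at Day 28 of Cycle 3, at Day 28 of Cycles 6 and 9, and under "Completion of Study". That last column carries no day, cycle or month. A footnote allows one week either side of each required scan.

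**After treatment.** Section 14.4 plans at least a year of follow-up per patient but schedules no assessments. Section 16 covers only study length and record retention. Section 14.6 gives no censoring rule for PFS.

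**The concern.** The protocol treats twelve 28-day cycles and twelve months as the same length. They are not, and the gap widens with each scan. A reader who follows the table and one who follows the text would image the same patient on different days.

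Two results depend on this. For 12-month PFS, a patient who is progression-free at a final scan near the end of Cycle 12, with no later assessment, would by usual practice be censored there. If every remaining patient is censored before day 365, nobody is at risk at the landmark. The reported figure would then be an 11-month value carried forward, or not estimable. For the 6-month endpoints, the Cycle 6 scan comes before 6 months have passed. Stable disease at that scan does not by itself show 6 months of stable disease, and the table's next scan is three cycles later. Patients scanned under the two rules could be classified differently on the primary endpoint.

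**Working it through.** **The plan's own figures.** The documents give no day number for any scan, so there is nothing to reproduce on this point. The only design calculation is the Section 14.4 table, the chance of at least one event in 10 patients. 1 − (1 − p)^10 gives 0.4013, 0.6513, 0.8031, 0.8926, 0.9437 and 0.9718, which matches the stated values. It does not bear on scan timing.

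**Inputs.** Cycle length 28 days (Section 4.2); scans at Cycles 3, 6 and 9 plus an undated final scan (Section 7 table); scans every 3 months (Section 7 text); a 7-day window either side under both rules; one month = 365.25 / 12 = 30.44 days; eleven patients (Section 6).

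**Scan days.** Table rule: 28 × cycle number. Text rule: 30.44 × month number, rounded to whole days.

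| Scan | Table rule (window) | Text rule (window) | Difference | Windows overlap? |
|---|---|---|---|---|
| 1 | 3 × 28 = 84 (77–91) | 91 (84–98) | 7 days | Yes |
| 2 | 6 × 28 = 168 (161–175) | 183 (176–190) | 15 days | No |
| 3 | 9 × 28 = 252 (245–259) | 274 (267–281) | 22 days | No |
| 4, if taken at the end of Cycle 12 | 12 × 28 = 336 (329–343) | 365 (358–372) | 29 days | No |

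The nearest edges are 1 day apart at scan 2 (175 and 176), 8 days apart at scan 3 (259 and 267) and 15 days apart at scan 4 (343 and 358).

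**Distance to the landmarks under the table.** The Cycle 6 scan falls 183 − 175 = 8 to 183 − 161 = 22 days before 6 months. A final scan at the end of Cycle 12 falls 365 − 343 = 22 to 365 − 329 = 36 days before 12 months.

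**Effect of the cycle window.** If every cycle ran 3 days long, Cycle 6 would end on day 6 × 31 = 186 and Cycle 12 on day 12 × 31 = 372. If every cycle ran 3 days short, they would end on days 6 × 25 = 150 and 12 × 25 = 300. Drift can therefore close the gap or widen it.

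**Size of the bias.** Assume exponential PFS with true 12-month value p. The value at day 336 is p^(336/365.25):

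- p = 0.10 gives 0.120
- p = 0.20 gives 0.228
- p = 0.30 gives 0.330
- p = 0.50 gives 0.529

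That is 2 to 3 points too high. Reading day 168 as 6 months involves the same ratio: 0.20 becomes 0.228, 0.40 becomes 0.431 and 0.50 becomes 0.529. For scale, one patient in eleven is 1/11 = 9.1 points, and the exact 95% interval for 2 of 11 is about 2% to 52%.

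**The case against.** A reader might infer that the last MRI is scheduled for day 336 and that no patient is imaged at 12 months. The documents do not support that.

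- **Day 336 is an inference.** No MRI is listed at Cycle 12. The TSH and pregnancy-test rows are marked at Cycle 12 and again at completion, so completion may be a separate, later visit.
- **Other passages point to about day 365.** The 3-monthly rule puts the fourth scan there, therapy may run up to 12 months, and at least a year of follow-up is planned.
- **Cycles can run late.** Each new cycle depends on laboratory criteria, and Section 7.1 provides for holds of 14 days or more. The documents do not say whether holds extend the cycle calendar. If they do, two 14-day holds put the end of Cycle 12 at day 336 + 28 = 364.
- **PFS does not rest on imaging alone.** Section 13 also counts clinical deterioration, and failure to return because of death or deterioration, as progression. The 12-month survival aim requires vital status to month 12. Only silent radiographic progression is likely to go unseen.
- **The numerical effect is small.** It is under a third of one patient. Section 2 puts mortality in recurrent disease near 100%, so few patients may reach the end of Cycle 12 progression-free.

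All of this stands, and it limits the claim. It does not remove the conflict between the two scan rules. Nothing dates the final scan, and even a scan that complies with the text may fall on days 358 to 364, before the landmark. The 6-month mismatch needs no inference about completion, because the Cycle 6 scan is explicitly tied to its cycle.

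**Conclusion.** The concern holds as an internal inconsistency. On exact 28-day cycles the second and third scans cannot meet both rules, although at the second scan a single day of slippage would let the windows touch. The Cycle 6 scan precedes 6 months by 8 to 22 days. A 12-month PFS assessment is possible but not secured: if the undated final scan is taken at the end of Cycle 12, imaging ends 22 to 36 days early.

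The 2-to-3-point bias rests on an assumed exponential curve and on PFS being read at the earlier day. It is well inside the sampling error for eleven patients. The reasons to act are whether the 12-month figure can be estimated at all, whether its label is accurate, and whether the primary 6-month criterion is applied alike to every patient.

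**What to change.** Reconcile the text and table of Section 7 into one MRI calendar numbered in days from first dose. Place the 6-month scan, and the final scan for progression-free patients, at or just after 6 and 12 calendar months. For example, use nominal days 91, 183, 274 and 365, with windows at 183 and 365 that run forward only. Re-date the whole row: moving only the final scan would leave 365 − 252 = 113 days after the Cycle 9 scan, beyond the protocol's own 91 + 7 = 98.

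Alternatively, keep the cycle-based scans and change the text to every 12 weeks (3 × 28 = 84 days). Date the final scan at the end of Cycle 12, and restate the 6- and 12-month disease-control and PFS landmarks in Sections 3 and 14.6 as 24 weeks (168 days) and 48 weeks (336 days).

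Under either option, state in Section 14.6 how PFS is censored. Whether therapy runs for twelve cycles or twelve months should be reconciled separately by the sponsor.

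The cost is a small schedule edit or slightly shorter stated landmarks, with no additional scan. Neither option supplies imaging for patients who stop for toxicity without progression.
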